6.3 Drug logistics and accountability

All study drugs will be stored at the investigational site in accordance with Good Clinical Practice (GCP) and Good Manufacturing Practices (GMP) requirements and the instructions given by the clinical supplies department of the Institution and will be inaccessible to unauthorized personnel.

6.3.1 Accountability

The investigator, or a responsible party designated by the investigator, must maintain a careful record of the inventory and disposition of the agent(s) (investigational or free of charge) using the NCI Drug Accountability Record or another comparable drug accountability form. (See the CTEP website at <http://ctep.cancer.gov/protocolDevelopment>

for the “Policy and Guidelines for Accountability and Storage of Investigational Agents” or to obtain a copy of the drug accountability form.)

6.3.2 Destruction and Return

At the end of the study, unused supplies of Ra 223 dichloride and other investigational agents should be destroyed appropriately and according to institutional policies. Destruction will be documented in the Drug Accountability Record Form. The certificate of destruction for Ra 223 dichloride should be sent to Bayer.

6.4 Treatment compliance

Subject compliance with the treatment and protocol includes willingness to comply with all aspects of the protocol, and to have blood collected for all safety evaluations. At the discretion of the principal investigator, a subject may be discontinued from the trial for non-compliance with follow-up visits or study drug.

6.5 Prior and concomitant therapy-

All medication that is considered necessary for the subject’s welfare, and which is not expected to interfere with the evaluation of the study treatment, may be given at the discretion of the investigator. All medications (including contrast media) taken within 2 weeks prior to the start of the study and during the study must be recorded in the subject’s source documentation and in the CRF (including start/stop dates, dose frequency, route of administration, and indication).

Permitted

- Treatment with non-conventional therapies (e.g., herbs [with the exception of St. John’s Wart], acupuncture) and vitamin/mineral supplements is acceptable provided that, in the opinion of the investigator, such treatment will not interfere with the trial endpoints.
- Subjects may receive standard of care for any underlying illness.
- In the event of neutropenia, anemia, or thrombocytopenia, subjects may receive appropriate supportive care (e.g., transfusion, biologic response modifiers such as G-CSF or GM-CSF, prophylactic antibiotics, antifungals and/or antivirals, hematopoietic growth factors).
- Blood transfusions and erythropoietin are allowed.
- If surgery is required during study drug treatment, the surgeon needs to be notified that the patient has been treated with a radioactive product and adequate precautions for radioactive protection should be applied during the surgical procedure. The patient should continue with study treatment if considered safe in the treating Investigator’s opinion.
- Concomitant treatments for prostate cancer will be recorded in the CRFs.

7. Procedures and variables

“The values in this protocol have been revised as per the United States (US) National Institute of Standards and Technology (NIST) standardization update (agreed on 17 MAR 2015)”

7.1 Schedule of procedures

7.1.1 Tabulated overview

Table 1: Treatment	S	B	T1 D 1	T1 D 4	T 2	T3	T 4	T 5	T 6	F/ U 1M	F/ U 4M	F/U 18 M
History & physical exam	X		X		X	X	X	X	X	X	X	X
^{99m} Tc MDP bone scan	X					X ¹					X	
CT a/p	X					X ^{1, 2}					X	
Fluciclovine PET/MRI ³		X				X ¹						
Medication history	X		X		X	X	X	X	X	X	X	X
Chemistry panel	X		X		X	X	X	X	X	X		
CBC with differential	X		X		X	X	X	X	X			
PSA			X		X	X	X	X	X	X	X	X
CTCs by CellSearch ⁴			X		X	X						
CTCs by microfluidic chip ⁵				X		X	X					
BAP & NTx			X	X	X	X	X	X	X	X	X	X
Blood biomarkers ⁶			X	X	X	X	X	X	X	X	X	X
Patient reported outcomes ⁷				X		X	X	X	X	X	X	X
Adverse event reporting				X		X	X	X	X	X		

Notations:

Screening studies “S” must be done within 60 days of start of treatment (“T1 D1”).

Baseline study “B” must be done after a subject is successfully registered to the trial, but prior to start of treatment (“T1 D1”).

Treatments T1 through T6 occur at 4 week intervals \pm 7 days.

(1) T3 timepoint scans (bone scan, and CT a/p, and fluciclovine PET/MRI in some) will be performed within 10 days prior to the T3 treatment day.

(2) T3 timepoint CT a/p will be performed only for participants that do not undergo fluciclovine PET/MRI.

(3) fluciclovine PET/MRI will be performed at two timepoints each for 10 of the study participants. They will be chosen by investigator discretion in light of their willingness and medical eligibility to undergo PET/MRI (e.g. pacemaker is a contraindication, claustrophobia is a contraindication). The baseline PET/MRI will only be done after the subject has successfully been registered to the trial, but prior to start of treatment (“T1 D1”).

(4) CTCs, circulating tumor cells; 7.5 mL of whole blood will be collected in a special CellSave tubes as described in Appendix G for BWH core lab testing using the commercially available Veridex CellSearch assay; subsequent CTC testing will only be carried out on participants who had ≥ 1 detectable CTC on study T1 D1.

(5) 20 mL of blood will be collected in vacutainer tubes (usually purple top EDTA tubes) for [name]/[name] laboratory analysis of circulating tumor cells as detailed in Appendix B;

subsequent CTC testing will only be carried out on participants who had ≥ 1 detectable CTC on study T1 D1.

(6) Plasma biomarkers; 10 mL of blood will be collected in a purple top (EDTA plasma) tube and processed as detailed in Appendix C for batched analysis of inflammatory and angiogenic biomarkers.

(7) Analgesic use and other patient reported outcomes will be collected as detailed in Appendices D, E, and F.

Abbreviations:

S, screening; B, baseline;

T1 D1, Ra-223 treatment 1 day 1;

F/U 1M, follow-up visit 1 month after final Ra-223 treatment;

F/U 4M, follow-up visit 4 months after final Ra-223 treatment;

F/U 18M, follow-up visit 18 months after final Ra-223 treatment;

CT a/p, CT of the, abdomen, and pelvis;

Chemistry panel, includes liver panel also known as LFTs; CBC, complete blood count;

PSA, serum prostate specific antigen;

PET, positron emission tomography;

CTCs, circulating tumor cells;

BAP, bone-specific alkaline phosphatase; NTx, n-telopeptide.

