“The values in this protocol have been revised as per the United States (US) National Institute of Standards and Technology (NIST) standardization update (agreed on 17 MAR 2015)”

Erythema, pain, and edema at the injection site were reported in 1% of patients on Radium Ra 223 dichloride.

Secondary malignant neoplasms

No cases of radiation-induced cancer have been reported in clinical trials with radium-223 dichloride in follow-up of up to three years. However, the radiation dose resulting from therapeutic exposure may result in higher incidence of cancer (e.g. sarcomas of the bone, or leukemia), mutations and a potential for development of hereditary defects.

Bone Marrow Suppression

In the randomized trial, 2% of patients on the Radium Ra 223 dichloride arm experienced bone marrow failure or ongoing pancytopenia compared to no patients treated with placebo. There were two deaths due to bone marrow failure and for 7 of 13 patients treated with Radium Ra 223 dichloride, bone marrow failure was ongoing at the time of death. Among the 13 patients who experienced bone marrow failure, 54% required blood transfusions. Four percent (4%) of patients on the Radium Ra 223 dichloride arm and 2% on the placebo arm permanently discontinued therapy due to bone marrow suppression.

In the randomized trial, deaths related to vascular hemorrhage in association with myelosuppression were observed in 1% of Radium Ra 223 dichloride-treated patients compared to 0.3% of patients treated with placebo. The incidence of infection-related deaths (2%), serious infections (10%), and febrile neutropenia (<1%) were similar for patients treated with Radium Ra 223 dichloride and placebo.

Myelosuppression; notably thrombocytopenia, neutropenia, pancytopenia, and leukopenia; has been reported in patients treated with Radium Ra 223 dichloride. In the randomized trial, complete blood counts (CBCs) were obtained every 4 weeks prior to each dose and the nadir CBCs and times of recovery were not well characterized. In a separate single-dose phase 1 study of Radium Ra 223 dichloride, neutrophil and platelet count nadirs occurred 2 to 3 weeks after Radium Ra 223 dichloride administration at doses that were up to 1 to 5 times the recommended dose, and most patients recovered approximately 6 to 8 weeks after administration

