Hematologic evaluation of patients must be performed at baseline and prior to every dose of Radium Ra 223 dichloride. Before the first administration of Radium Ra 223 dichloride, the absolute neutrophil count (ANC) should be $\geq 1.5 \times 10^9/L$, the platelet count $\geq 100 \times 10^9/L$ and hemoglobin $\geq 10 \text{ g/dL}$. Before subsequent administrations of Radium Ra 223 dichloride, the ANC should be $\geq 1 \times 10^9/L$ and the platelet count $\geq 50 \times 10^9/L$. If there is no recovery to these values within 6 to 8 weeks after the last administration of Radium Ra 223 dichloride, despite receiving supportive care, further treatment with Radium Ra 223 dichloride should be discontinued. Patients with evidence of compromised bone marrow reserve should be monitored closely and provided with supportive care measures when

clinically indicated. Discontinue Radium Ra 223 dichloride in patients who experience life-threatening complications despite supportive care for bone marrow failure.

The safety and efficacy of concomitant chemotherapy with Radium Ra 223 dichloride have not been established. Outside of a clinical trial, concomitant use with chemotherapy is not recommended due to the potential for additive myelosuppression. If chemotherapy, other systemic radioisotopes or hemibody external radiotherapy are administered during the treatment period, Radium Ra 223 dichloride should be discontinued.

2. Study objectives

The primary objective of this study is to evaluate the quantitative effect of Ra-223 on ^{99m}Tc-MDP bone scan in men with castration-resistant prostate cancer metastatic to bone. .

Secondary objectives include the description of mean percent change in bone scan lesion area by 18-month survival status as well as the evaluation of the effects of Ra-223 by the following measures:

(A) Imaging biomarkers

- I. Concurrent conventional assessments including Computed Tomography scans
- II. Baseline assessments including fluciclovine PET (if assigned to PET), ^{99m}Tc MDP bone scan, & blood testing

(B) Standard and novel circulating tumor cell assays

- I. CTC number by FDA-approved assay (Veridex CellSearch)
- II. CTC translational biomarkers by microfluidic platform
 - (e.g. enumeration, androgen receptor signaling, proliferative index by Ki67 staining)

(C) Circulating biomarkers of the tumor microenvironment

- I. Bone turnover markers (serum bone specific alkaline phosphatase, N-telopeptide)

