5.2.3 Duration of Follow-up

Participants will be followed for 18 months after removal from protocol therapy or until death, whichever occurs first. Participants removed from protocol therapy for unacceptable adverse event(s) will be followed until resolution or stabilization of the adverse event.

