6.2.8 Dose Modification/Delays

Every effort should be made to administer the full dosing regimen of Radium Ra 223 dichloride. Adjustment of dose level is not permitted.

Study visits during the treatment period will occur at protocol-defined intervals (within a window of +/- 7 days).

Dosing delays may be instituted under the following circumstances:

Disease progression: The Investigator should delay cytotoxic chemotherapy, other systemic radioisotope, hemibody external radiotherapy or other investigational drug until the follow-up period. If such treatments have to be given during the treatment period, further study drug administrations must be discontinued. Patients with disease progression may continue treatment at the Investigator's discretion.

Myelosuppression: Treatment-related changes in hematology parameters may occur.

- If a patient experiences CTCAE v4.03 Grade 3 or 4 neutropenia, thrombocytopenia, or anemia the administration of study drug should be delayed until recovery to Grade 2 or better.
- If a patient experiences CTCAE v4.03 Grade 3 or 4 neutropenia, thrombocytopenia, or anemia lasting > 14 days, further study drug administrations must be discontinued.
- Blood transfusion is acceptable. Use of biologic response modifiers, such as G-CSF or GM-CSF, is allowed in the management of acute toxicity.

Gastrointestinal events: Diarrhea should be treated as per local practice. A further dose of study medication should not be given before diarrhea is recovered to CTCAE v4.03 Grade 2 or baseline levels. Nausea or vomiting should be treated as per local practice. A further dose of study medication should not be given before nausea or vomiting is recovered to CTCAE v4.03 Grade 2 or baseline levels.

Spinal Cord Compression: If the patient experiences spinal cord compression during the treatment period, the patient should be treated for the event, and may receive further study drug administration if adequately recovered.

Surgical Intervention: If surgery is required, the patient should continue with study treatment, if this is considered safe in the treating Investigator's opinion. The surgeon needs to be notified that the patient has been given radioactive drug, and needs to follow the guidelines for radioactive protection.

Non-Pathological Fractures: For traumatic fractures in weight-bearing bones during treatment phase, the study drug administration should be delayed for 2-4 weeks from the time of fracture.

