7.15.1.3 Assessments and documentation of adverse events

7.15.1.4 Reporting of serious adverse events

The definition of serious adverse events (SAEs) is given in Section 7.15.1.1.

Each serious adverse event must be followed up until resolution or stabilization, by submission of updated reports to the designated person. An isolated laboratory abnormality that is assigned grade 4, according to CTC definition, is not reportable as an SAE; unless the investigator assesses that the event meets standard ICH criteria for an SAE. CTC grade 4 baseline laboratory abnormalities that are part of the disease profile should not be reported as an SAE, specifically when they are allowed or not excluded by the protocol inclusion/exclusion criteria.

When required, and according to local law and regulations, serious adverse events must be reported to the Ethics Committee and Regulatory Authorities.

All serious adverse events should be reported to Bayer within 24 hours. In the event of such an event, the investigator should refer to the Pharmacovigilance section of the contract for reporting procedures.

Requirements for Reporting of Serious Adverse Events:

All SAEs must be reported to Bayer within 24 hours of the Principal Investigator's awareness and must include the following minimum information:

1. The name and contact information of the reporter
2. The name of the study drug(s)
3. A description of the reported SAE
4. A patient identified by one or more of the following:
 - a. Patient initials
 - b. Patient number
 - c. Knowledge that a patient who experienced the adverse event exists
 - d. Age
 - e. Sex
5. An investigator assessment of study drug causality. For studies with combination therapy, a separate causality assessment should be provided for each study drug.

Additional data which would aid the review and causality assessment of the case include but are not limited to:

The date of onset

The severity

The time from administration of study drug(s) to start of the event

The duration and outcome of the event

Any possible etiology for the event

The final diagnosis or syndrome, if known

The Investigator may report serious adverse drug reactions (SADRs) using either:

An ADEERS form (Adverse Event Expedited Reporting System) available at

<http://ctep.cancer.gov/reporting/adeers.html>

OR

A MedWatch form available at <http://www.fda.gov/medwatch/>

All reports shall be sent electronically to:

Electronic Mailbox: [contact]

[contact]

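### As the schedule reads, no blood count is planned after the sixth Ra-223 dose, although chemistry is drawn one month later; a CBC at F/U 1M would close this minor safety gap cheaply

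*Combined protocol and SAP*

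**What the plan says.** Table 1 in Section 7.1.1 is the only place where visits are fixed; Section 7.1.2 refers all timing back to it. Its row "CBC with differential" is marked at S, T1 D1, T2, T3, T4, T5 and T6, and is blank at F/U 1M, F/U 4M and F/U 18M. The chemistry row carries the same marks and one more, at F/U 1M. The abbreviations define that visit: "F/U 1M, follow-up visit 1 month after final Ra-223 treatment". History and physical exam is marked at all three follow-up visits.

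Section 1.3.5 states the hematology requirement: "Hematologic evaluation of patients must be performed at baseline and prior to every dose of Radium Ra 223 dichloride". The same section reports, from a separate single-dose phase 1 study at up to 1 to 5 times the recommended dose, neutrophil and platelet nadirs at 2 to 3 weeks, and that "most patients recovered approximately 6 to 8 weeks after administration". Of the randomized trial, which took counts before each dose, it says that "the nadir CBCs and times of recovery were not well characterized".

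Section 6.2.8 ties cytopenia to the next dose: in a patient with "Grade 3 or 4 neutropenia, thrombocytopenia, or anemia the administration of study drug should be delayed until recovery to Grade 2 or better". Section 5.2.3 adds: "Participants removed from protocol therapy for unacceptable adverse event(s) will be followed until resolution or stabilization of the adverse event". Section 7.15.1.4 follows serious adverse events to resolution or stabilization, but says that "An isolated laboratory abnormality that is assigned grade 4, according to CTC definition, is not reportable as an SAE", unless the investigator judges that it meets the ICH criteria.

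**The concern.** Marrow suppression is a main toxicity in the protocol's own summary of this drug. Section 1.3.5 reports bone marrow failure or ongoing pancytopenia in 2% of treated patients and in none on placebo. Doses 1 to 5 are checked because a further dose follows. After the sixth there is no further dose, and the count disappears from the schedule even though blood is still drawn one month later.

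The man this affects is one with acceptable counts at his last pre-dose check, who then develops a cytopenia without symptoms, or fails to recover from one. Under the schedule he is found only if symptoms appear or someone orders an unscheduled count. Two things are at stake: his own care, since later therapy is left to the treating oncologist (Section 4), and complete safety data on the last dose. Section 7.15 names blood counts among the possible safety variables, and the DSMB reviews toxicity (Section 9.2).

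**Working it through.** The plan states no figure to reproduce here. The check is a comparison of schedule rows, followed by simple timing arithmetic.

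**1. The two laboratory rows (Table 1, Section 7.1.1)**
- CBC: S, T1 D1, T2, T3, T4, T5, T6 = 7 marks, of which 0 fall after the T6 visit.
- Chemistry: the same 7 plus F/U 1M = 8 marks, of which 1 falls after the T6 visit.
- The rows agree at every visit through T6 and differ only at F/U 1M.

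**2. Which doses are followed by a scheduled count**
- Doses are 4 weeks apart, plus or minus 7 days (notes to Table 1). The pre-dose count at the next treatment visit therefore falls 4 - 1 = 3 to 4 + 1 = 5 weeks after the previous dose.
- This covers each of doses 1 to 5 that is followed by another dose.
- A planned sixth dose is followed by F/U 1M, 4M and 18M, none with a CBC mark. The last scheduled count is at the T6 visit itself (week 0).
- If a man stops early, a count may exist from the visit where his next dose was withheld. Table 1 alone does not settle this.

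**3. Whether other provisions order the count**
- Section 6.2.8 delays or stops a further dose. After the last one it has nothing to act on.
- Section 5.2.3 reaches men removed for unacceptable adverse events, not a man who completes six doses with acceptable counts.
- Section 7.15.1.4 acts on events already found, and an isolated grade 4 laboratory value does not by itself count as serious.
- Section 7.15.1 includes laboratory tests in adverse event monitoring, and Section 1.3.5 asks for close monitoring when marrow reserve is compromised. Neither sets a time after the last dose.
- The exams at F/U 1M, 4M and 18M give an opportunity to order a count but do not require one.

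**4. What a count at F/U 1M (about week 4) would and would not show**
- Against the reported nadir at weeks 2 to 3: 4 - 3 = 1 to 4 - 2 = 2 weeks after it.
- Against the reported recovery at weeks 6 to 8: 6 - 4 = 2 to 8 - 4 = 4 weeks before it.
- It would therefore detect cytopenia still present at about week 4. It would not measure the nadir or the time to recovery.

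**5. Size**
- At most one unscheduled count per man, so up to 22 in the trial.
- No expected number of cases can be derived. Table 2 in Section 1.3.5 rests on values at baseline and before each cycle, so it gives no rate after a final dose.

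**6. Reliability of the table**
- In the extracted text, some other rows look displaced by a column (CTCs by microfluidic chip, patient reported outcomes, adverse event reporting).
- The agreement of the CBC and chemistry rows through T6 argues against a shift of the CBC row. It cannot exclude a single lost mark at F/U 1M, though nothing positive suggests one.

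**The case against.** The strongest reply is that the schedule does what the protocol requires. Section 1.3.5 asks for counts at baseline and before each dose, and Table 1 provides them. Pre-dose counts exist to decide on the next dose, and after T6 there is none to decide on. This is a biomarker study of standard-of-care treatment, with no safety objective in Section 2. A clinician sees the man at F/U 1M, 4M and 18M and can order a count; as read, Table 1 also marks adverse event reporting at F/U 1M. All of this stands. It makes the change an improvement rather than the repair of a breach. It does not supply a scheduled count: chemistry is just as routine, yet the protocol schedules it at F/U 1M.

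Three stronger readings are tempting, and the documents support none of them.
- A reader might infer that the schedule repeats the randomized trial's failure to characterize nadir and recovery, and that a CBC at F/U 1M would cure it. That limitation arose with counts every 4 weeks, and a count at about week 4 keeps the same interval. The nadir and recovery times also come from a single-dose study at up to 1 to 5 times the recommended dose.
- A reader might infer that no man has a count after his last dose. A man whose next dose is withheld for cytopenia has already been counted, and the Section 6.2.8 rule on cytopenia lasting more than 14 days implies repeat counts. The gap is certain only for a planned sixth dose.
- A reader might turn the share of doses without a later count into a risk. That share only restates that one dose is the last, and carries no information on how often cytopenia follows it.

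**Conclusion.** The point holds as a minor safety gap with a cheap remedy. As read, Table 1 schedules no count after a planned sixth dose, while it schedules chemistry one month later and gives earlier doses a count 3 to 5 weeks on. Silent cytopenia after the last dose, in a man whose last pre-dose count was acceptable, is therefore not systematically measured. The protocol's stated hematology requirement is not breached, and neither the bone scan endpoint nor the sample size is affected.

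The conclusion assumes that the blank at F/U 1M in the CBC row is real. For men who stop early, it depends on whether a count was taken when dosing was withheld. How many men would be found with Grade 3-4 values cannot be stated from the documents.

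**What to change.** 1. Check the CBC row against the laid-out table in the source protocol. If the F/U 1M mark is there, nothing further is needed on the schedule.
2. If it is absent, add a "CBC with differential" mark at F/U 1M.
3. Add a sentence along these lines: *Grade 3-4 neutropenia, thrombocytopenia or anemia found at F/U 1M is followed with repeat counts until Grade 2 or better, or until stable.* These are the three cytopenias that Section 6.2.8 acts on. The clinical team should confirm the choice.

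The cost is one routine tube per man, up to 22 tubes, with no new visit. Chemistry alone already secures a blood draw at F/U 1M, and Table 1 also marks PSA, bone turnover markers and blood biomarkers there. Occasional repeat counts would follow, limited to men with Grade 3-4 values. The gain is that the last dose gets the same check at roughly 4 weeks as the earlier ones; the protocol should not claim more for it than that.

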Time to first SRE (defined as time to EBRT, time to first pathological bone fracture, time to spinal cord compression and time to surgical intervention) was statistically significantly longer in the radium-223 chloride group compared to placebo (median number of months=15.6 for radium-223 chloride versus 9.8 months for placebo (HR=0.658, 95 CI 0.522–0.830, p= 0.00037).

Time to total ALP progression (defined as $\geq 25\%$ increase compared to baseline/nadir) was statistically significantly longer in the radium-223 chloride group 7.4 months compared to placebo 3.8 months (HR = 0.167, 95% CI 0.129 – 0.217; p= <0.00001).

Time to PSA progression (defined as a $\geq 25\%$ increase and an increase in absolute value of ≥ 2 ng/mL compared to baseline/nadir) was also significantly prolonged in patients receiving Radium Ra 223 dichloride compared to patients receiving placebo (HR = 0.643, 95% CI 0.539,0.768; p = <0.00001)

A total ALP response (defined as a confirmed $\geq 30\%$ or $\geq 50\%$ reduction compared to baseline) at week 12 was observed in higher proportions of subjects who were treated with radium-223 chloride group (47% and 3% respectively) compared to those in the placebo (3% and <1% respectively) group.

Subgroup survival analysis showed a consistent survival benefit for treatment with Radium Ra 223 dichloride, independent of total alkaline phosphatase (ALP), current use of bisphosphonates, prior use of docetaxel and baseline ECOG status. The results from the phase III ALSYMPCA study regarding time to external beam radiation therapy (EBRT) for pain relief and fewer patients reporting bone pain as an adverse event in the Radium Ra 223 dichloride group indicate a positive effect on bone pain.

The most common adverse reactions ($\geq 10\%$) in patients receiving Radium Ra 223 dichloride were nausea, diarrhea, vomiting, and peripheral edema (Table 1). Grade 3 and 4 adverse events were reported among 57% of Radium Ra 223 dichloride-treated patients and 63% of placebotreated patients. The most common hematologic laboratory abnormalities in Radium Ra 223 dichloride-treated patients ($\geq 10\%$) were anemia, lymphocytopenia, leukopenia, thrombocytopenia, and neutropenia (Table 2). Treatment discontinuations due to adverse events occurred in 17% of patients who received Radium Ra 223 dichloride and 21% of patients who received placebo.

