Bone scans are scheduled for the beginning of month 3/end of month 2 (T3), and one month post month 6 (FU1M). Descriptive statistics on absolute and percent change in BSA from baseline to these study timepoints will be provided for the overall study cohort and within survivor groups. By the end of month 2, bone scan response is expected in 35% of subjects. Patients will be cross-classified by bone scan response status at 2 months and survival status at 18 months. Agreement will be quantified using Cohen's Kappa; however, the sample size is too small to produce a realistic confidence interval. Kappa is assessed as follows: <0.00, poor; 0.00-0.20, slight; 0.21-0.40, fair; 0.41-0.60, moderate; 0.61-0.80, substantial; 0.81-1.00, almost perfect; and 1.00, perfect. Survival time defined as the time from registration to death, or if censored to date last known alive will be calculated. Correlation between change in BSA after 2 months and survival time will be assessed graphically with scatter plots and using Pearson correlation coefficient. Survival distributions will also be estimated using the Kaplan-Meier method in a landmark analysis at 2 months. Survival time is defined as the time from response classification (at 2 months) to death, or if censored to date last known alive. Cox proportional hazards (PH) regression will be used to estimate the bone scan response hazard ratio along with 95% confidence limits.

This study also affords insights into several other potential biomarkers including measures related to circulating tumor cells (number, proliferative index, AR signaling, markers of DNA damage/repair), bone turnover (BAP, NTx), inflammation and angiogenesis. Fluciclovine PET imaging will occur in 10 subjects at baseline and the end of month 2 of treatment. All other measures will occur at baseline, during treatment, and post treatment as detailed in the required data table. Descriptive statistics will be provided for each measure and timepoint along with absolute and percentage change from baseline. Association with overall survival and response will be analyzed as exploratory similar to the methods above for bone scan.

Accrual Targets

Accrual Targets						
Ethnic Category	Sex/Gender					
	Females		Males		Total	
Hispanic or Latino	0	+	1	=	1	
Not Hispanic or Latino	0	+	21	=	21	
Ethnic Category: Total of all subjects	0	(A1)	+	22	(B1) = 22 (C1)	
Racial Category						
American Indian or Alaskan Native	0	+	0	=	0	
Asian	0	+	1	=	1	

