Black or African American	0	+	1	=	1	
Native Hawaiian or other Pacific Islander	0	+	0	=	0	
White	0	+	20	=	20	
Racial Category: Total of all subjects	0	(A2)	+	22	(B2) = 22 (C2)	
	(A1 = A2)		(B1 = B2)		(C1 = C2)	

Timeline

We anticipate an average of 2 subjects to be accrued monthly (approximate accrual time: 12 months). The primary endpoint (assessment of change in total area of bone metastases by ^{99m}Tc MDP bone scan) is assessed 2 months after the start of treatment; the primary analysis will take place 14 months after study activation. With an anticipated 12 month enrollment period and per-subject 18 months of study-directed treatment and follow-up, the last enrolled patient will conclude follow-up 30 months after activation.

Notable anticipated dates and analyses are as follows:

- T: 0m Study opens for accrual at MGH
- T: 12m Study accrual completed
- T: 14m Primary analysis
- T: 30m Completion of all study follow-up

9. Data handling and quality assurance

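### The month-2 primary bone scan is scheduled only against the dose-3 day, so a patient who stops dosing earlier but stays in follow-up has no scheduled scan for the primary endpoint

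*Combined protocol and SAP*

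**What the plan says.** Sections 7.14 and 8 define bone scan response as a fall of at least 30% in bone scan lesion area from baseline to the end of month 2, after two of the six planned doses. The Timeline in Section 8 says that the primary endpoint "is assessed 2 months after the start of treatment".

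The schedule is in Section 7.1.1, and Section 7.1.2 refers all timing back to its notes. The bone scan is marked at screening, T3 and F/U 4M. Note (1) says that the T3 scan "will be performed within 10 days prior to the T3 treatment day". On dosing, "Treatments T1 through T6 occur at 4 week intervals", with a 7-day tolerance. The follow-up visits count from the last dose: "F/U 1M, follow-up visit 1 month after final Ra-223 treatment" and "F/U 4M, follow-up visit 4 months after final Ra-223 treatment".

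Section 8, Secondary Aims, gives another schedule: "Bone scans are scheduled for the beginning of month 3/end of month 2 (T3), and one month post month 6 (FU1M").

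Section 6.2.8 requires some patients to stop. For grade 3 or 4 cytopenia the wording is "lasting > 14 days, further study drug administrations must be discontinued". Stopping dosing is not among the mandatory reasons for withdrawal in Section 5.2.2, and Section 5.2.3 follows patients for 18 months after protocol therapy ends. Section 5.2.5 allows no replacement. Section 8 enrols 22, assumes that 90% have adequate data, and states the go rule as 5 or more responses in 20.

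**The concern.** The endpoint is set in calendar time from the first dose, but the scan that measures it is set by a dose that some patients will not receive. The two agree only while dosing continues on schedule. A patient who stops before the window ahead of dose 3 is still available for imaging, yet the plan schedules no month-2 scan for him. The scans lost this way are not a random subset, because they belong to patients taken off treatment early.

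If those patients respond less often, a response rate among scanned patients is too high. The same patients drop out of the secondary analyses that relate the month-2 scan to survival: the two-sample t-test, the kappa table and the month-2 landmark analysis.

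A separate mismatch affects the later scan. The descriptive analysis of change in lesion area names FU1M, a visit at which the table schedules no bone scan.

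**Working it through.** **1. The plan's own design figure.** Exact binomial tails for 5 or more of 20 are 0.043 at a true rate of 10% and 0.882 at 35%. The printed table has 0.04 and 0.88, so it reproduces.

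**2. When the scan falls.** Take T1 D1 as week 0, T2 as week 4, T3 as week 8 and one month as 4.35 weeks.

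- On schedule, T3 is day 56 and the scan window is days 46 to 56.
- Last dose T1: F/U 4M = 0 + 4 × 4.35 = week 17.4.
- Last dose T2: F/U 4M = 4 + 4 × 4.35 = week 21.4 (20.4 to 22.4 with the 7-day tolerance).

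Neither is near week 8, so the F/U 4M scan cannot stand in for the month-2 scan.

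**3. How many patients.** The documents give no rate of stopping before dose 3. Section 1.3.5 gives two related figures from the phase III trial: 4% of radium patients stopped permanently for bone marrow suppression, and "Treatment discontinuations due to adverse events occurred in 17% of patients who received Radium Ra 223 dichloride". *Assumption:* stops are spread evenly over the five gaps between six doses, two of which come before dose 3. Then the share stopping before dose 3 is 1 − (1 − d)^(2/5).

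- d = 0.04: 1 − 0.96^0.4 = 0.016; × 22 = 0.4 patients.
- d = 0.17: 1 − 0.83^0.4 = 0.072; × 22 = 1.6 patients.

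The plan's allowance for inadequate data is 0.10 × 22 = 2.2 patients.

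**4. Effect on the reported rate.** Overstatement = share unscanned × (rate in scanned − rate in unscanned). *Assumption:* 35% in scanned patients (the plan's alternative), and 0 to 17.5% in unscanned ones.

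- Share 0.072: 0.072 × 0.35 = 2.5 points, or 0.072 × 0.175 = 1.3 points.
- Share 0.016: 0.016 × 0.35 = 0.6 points, or 0.016 × 0.175 = 0.3 points.

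**5. Effect on the go decision.** Removing non-responders from the denominator leaves the number of responders unchanged. A rule read as a fixed count of 5 is not affected.

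**The case against.** The strongest reply is that the plan already allows for this. Section 8 expects 10% without adequate data, the illustrated loss lies within that allowance, and the term evaluable suggests that unscanned patients are left out. The go count does not move, and at 5 of 20 the exact 95% interval is 8.7% to 49.1%, far wider than a bias of 1.3 to 2.5 points. Some patients stopped at the T3 visit will already have been scanned, and those who die or withdraw consent cannot be scanned under any schedule. All of this stands and limits the size. But the allowance sizes the trial. It does not schedule a scan or say how a missing one is counted.

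A second reply is that a patient given one dose cannot meet a definition that requires two. That also stands, and the plan should say where such patients belong.

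Three stronger readings are tempting, and the documents do not support them.

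- A reader might infer that Sections 7.1.1 and 8 conflict on whether a patient stopped after dose 2 is scanned near month 2, since FU1M counted from dose 2 is about week 8. But Section 8 describes that scan as a month after month 6, so on its own wording it is far from month 2. The mismatch concerns the later scan.
- A reader might place all 17% of discontinuations before dose 3. Nothing in the documents supports that timing.
- A reader might infer that the go rule is wrong. At 20 evaluable patients it is not. A count of 5 carries exact alpha of 5.2% at 21 evaluable and 6.2% at 22. With 22 enrolled and each independently 90% evaluable, alpha averages 4.25%.

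**Conclusion.** The gap is certain from the text: the primary scan has no anchor other than the dose-3 day, and a patient who stops before that window and stays in follow-up has no month-2 scan scheduled. The contradiction over the later scan, F/U 4M against FU1M, is equally plain.

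The size is unknown and probably small: 0.4 to 1.6 of 22 patients, and at the upper end an evaluable-only rate too high by 1.3 to 2.5 points. This rests on phase III discontinuation figures carried over to this trial, even spread over the dose gaps, and a lower response rate in unscanned patients. Stops for other reasons would add to it; patients already scanned before the T3 visit would subtract. This is a cheap improvement to the primary endpoint's completeness and does not challenge the sample size or the decision rule.

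**What to change.** 1. Amend note (1) in Section 7.1.1 so that the month-2 bone scan is due about 8 weeks after T1 D1, within a stated window, whether or not dose 3 is given. State how patients with only one dose fit a definition that refers to two of six doses. Change no dosing rule.
2. Reconcile the table and visit definitions in Section 7.1.1 with Section 8 on whether the later bone scan is at F/U 1M or F/U 4M.
3. In Section 8, report the response rate among all treated patients with a missing month-2 scan counted as non-response, alongside the evaluable rate.

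The cost is one schedule note and a few sentences. On the illustration above it means at most one or two scans in early stoppers, which are already planned for each patient. The all-treated rate will read slightly lower: with 7.2% unscanned and 35% response in the rest, 0.35 × (1 − 0.072) = 32.5%. The 5-of-20 rule needs no change.
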